4.8.3.2 Lymphocytes evaluation

All lymphocytes parameters (including markers of lymphocyte subtypes [T-, B-, and NK-cells]) but not be limited to CD19+, CD3+, CD4+, CD8+) will be summarized using absolute counts at each visit.

Corresponding listings will also be produced for lymphocyte parameters in infants and women.

Parameters may also be displayed graphically over time, as appropriate.

The primary endpoint analysis of the proportion of infants with B cell levels below the LLN is described in Section 4.4.1.

4.8.3.3 Serum antibody titers evaluation of infant

The secondary endpoint analysis of serum antibody (IgG) titers to immunization in the infant is described in Section 4.4.2.

4.8.4 Vital Signs

The actual value at each visit will be summarized for the following vital signs parameters in women: systolic blood pressure (mmHg), diastolic blood pressure (mmHg), pulse rate (beats/min), temperature (°C).

4.8.5 Neurological Examination

Neurological examination findings will be listed.

4.8.6 Pregnancy outcomes

The pregnancy outcomes including live births (term and preterm), therapeutic abortions and stillbirths will be calculated as follows:

- Pregnancy Interrupted (Yes/No)
- Type of pregnancy outcome (elective abortion, therapeutic abortion, stillbirth, live birth, not applicable)
- Details of interrupted pregnancy (Elective abortion, therapeutic abortion, stillbirth) If termination: reason for termination (prenatal testing finding, maternal health, psychosocial/nonmedical reasons, other)
- Details of non-interrupted live births (vaginal delivery (term), vaginal delivery (preterm), virginal delivery (forceps/vacuum – instrumental), cesarean (scheduled), cesarean (emergency)
- Gestational age at enrollment
- Gestational age at pregnancy termination
- Gestational age at live birth (absolute values as well as pre/full term)

Ocrelizumab—F. Hoffmann-La Roche Ltd

Statistical Analysis Plan MN42988

- Sex
- Singleton pregnancy
- Ultrasound abnormalities detected by trimester
- Presence of congenital anomalies

All pregnancy outcome details will be listed.

4.8.7 Concomitant Medications

Concomitant medications (defined as treatment started after baseline visit) will be summarized, for women and infants separately, by frequency tables according to the ATC classification system using the WHO Drug dictionary during pregnancy and during breastfeeding separately.

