3.1.3 Pregnancy and Early Postpartum Period

Mother:

- Pregnancy period: Laboratory and clinical assessments during the third trimester (gestational Week 35 [±14 days]) will be performed in accordance with planned prenatal care visits, whenever possible. To reduce the burden of visits on the mothers, results from physical and obstetric examinations, as well as neurological examinations, done as part of routine care may be used. *All* visit samples may be collected by home nurse visit. Women may be given vaccines (e.g., for *Bordetella pertussis*) as part of routine obstetric care (note: live or live-attenuated vaccines are not recommended during ocrelizumab treatment and until B-cells return to normal level). Ocrelizumab must not be administered after the woman is enrolled in the study and until the infant's birth. Should this happen, the woman will be discontinued from the study.
- Early postpartum period: A blood sample will be collected from the mother within 24 hours after delivery for assessment of serum ocrelizumab concentration. Treatment with commercial ocrelizumab may be resumed at any time after birth for women who decide not to breastfeed. Some women may decide to resume treatment with ocrelizumab whilst breastfeeding. For those women, treatment with ocrelizumab should be restarted after collection of the infant blood sample at Week 6 of life (±7 days) if possible, but the decision is left to the discretion of the woman and the investigator. If the woman switches to another DMT postpartum, the infant blood sample at Week 6 of life (±7 days) will only be collected if the woman is not breastfeeding.

Infant:

At birth, a blood sample will be collected from the umbilical cord (only for live births; no collection should occur in the event of a pregnancy interruption [i.e., therapeutic abortion

or stillbirth]). The target time frame for collection will be within 1 hour after delivery; the actual time of collection after delivery will be recorded. At Week 6 (\pm 7 days) of the infant's life, a blood sample will be collected from the infant (at an on-site visit, or by home nurse visit) for measurement of B-cell levels (the primary endpoint). For preterm infants, blood samples will be collected at the week of life equivalent to term infants (e.g., if birth occurred at gestational Week 35, blood sample would be collected at Week 8 of life).

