6.5 SAFETY ANALYSES

The safety analyses will be performed on the safety populations for the women and for the infants separately. The analyses will be conducted on data collected from enrollment until the end of the study.

The safety outcome measures will comprise the following: incidence and nature of all adverse events, including findings on vital sign measurements, neurological examinations, clinical laboratory tests, locally-reviewed MRIs conducted for safety reasons (non-MS CNS pathology), and concomitant medications.

Safety will be assessed through summaries of adverse events (including rates/incidence rates and corresponding 95% CIs) and clinical laboratory abnormalities.

All adverse events will be summarized by mapped term, appropriate thesaurus level and toxicity grade, and tabulated by MedDRA system organ class (SOC) and preferred term for individual adverse events within each SOC. Grade 3–5 adverse events, serious adverse event, adverse events leading to treatment discontinuation, and time to withdrawal from the study due to an adverse event will be summarized. In addition, all serious adverse events and deaths will be listed.

Associated laboratory parameters, such as hepatic function, renal function, and hematology values will be grouped and presented together.

The proportion of pregnancy outcomes including live births (term and preterm), therapeutic abortions and stillbirths will be calculated, and the corresponding two-sided Clopper-Pearson 95% CIs will be presented overall.

Concomitant medications recorded during the study will be summarized using frequency tables.

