4.3 DEMOGRAPHIC AND BASELINE CHARACTERISTICS

4.3.1 Women

The following demographic, MS history, baseline disease characteristics of women will be summarized and listed for the FASW, unless otherwise stated:

Demographic

- Age (years) as continuous and categorical (18–29, 30–40, >40)
- Self-reported race and ethnicity
- Education level
- Height (cm), weight (kg), and Body Mass Index (BMI: kg/m²)

- Smoking history (never, former)
- If previous smoker, time (years) since last use
- Alcohol use history (never, former)
- If previous user of alcohol, time (years) since last use

Multiple Sclerosis History

- Type of MS (relapsing-remitting multiple sclerosis [RRMS], secondary progressive multiple sclerosis [SPMS], primary progressive multiple sclerosis [PPMS], CIS)
- Duration (years) since onset of MS symptoms and its category (≤3 years, >3 to ≤5 years, >5 years to ≤10 years, >10 years to ≤15 years, >15 years)
- Duration (years) since MS diagnosis and its category (≤3 years, >3 to ≤5 years, >5 years to ≤10 years, >10 years to ≤15 years, >15 years)
- Expanded disability status scale (EDSS)
 - Change in EDSS score from last pre-baseline measurement (up to 1 year before LMP) to baseline
 - EDSS score:
 - Most recent prior to LMP: continuous and categorical (<2 vs \geq 2)
 - Last score prior to enrollment : continuous and categorical (<2 vs \geq 2)
- Relapses
 - Women with relapses up to 1 year prior to the LMP (yes, no)
 - Duration (Weeks) of most recent relapse and enrollment and its category (≤4 weeks, >4 and ≤8 weeks, >8 and ≤12 weeks, >12 and ≤16 weeks, >16 weeks)
 - Duration (months) between last onset of MS relapse up to one year prior to LMP and LMP and its category (≤6 months, >6 and ≤12 months)
 - Duration (months) between last onset of MS relapse after LMP prior to enrollment and enrollment and its category (≤6 months, >6 months)

If the date of the relapse is completely missing the relapse will be excluded from the analysis as appropriate. If only the year is available, it will be imputed to the first day of the year. If the day is missing, it will be imputed to the first day of the month.

Prior DMT Use

- Number of DMTs used prior to screening (1, 2, 3 and >3)
- Type of DMTs used prior to screening
- Number of women by the most recent DMT
- Reason for discontinuing most recent DMT

Ocrelizumab—F. Hoffmann-La Roche Ltd

Statistical Analysis Plan MN42988

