- Duration of the most recent DMT as continuous and categorical (≤6 months, >6 and ≤12 months, >12 and ≤24 months, >24 months)
- Time (months) from last DMT to first ocrelizumab infusion before enrollment
- Time (months) from last DMT to LMP

Prior Ocrelizumab Use

- Number and percentage of women received ocrelizumab in 3-month interval of before/during pregnancy (3-6 prior LMP, 0-3 month prior to LMP, 1st trimester)
- Time (months) between last ocrelizumab before LMP and LMP
- Time (months) between LMP and last ocrelizumab after LMP
- Received ocrelizumab after LMP (yes, no)
- Duration (months) of ocrelizumab therapy prior to enrolment
- Duration of ocrelizumab therapy prior to enrolment (≤6 months, >6 and ≤12 months, >12 and ≤24 months, >24 months)

Prior Medications

Prior medication (defined as treatment ended before LMP) and concurrent medications (defined as treatment started on or after the LMP) will be summarized, by frequency tables according to the Anatomic Therapeutic Chemical (ATC) classification system using the WHO Drug dictionary.

Baseline Disease Characteristics

- Baseline EDSS continuous and categorical (<2.5 vs ≥2.5)
- Baseline EDSS distribution: count and percent of patients corresponding to each observed score of EDSS at baseline
- Presence of any clinically significant abnormalities from the neurological examination (Yes, No)
- Type of neurological abnormality (disability progression independent of relapse, MS relapse, signs or symptoms suggestive of Progressive Multifocal Leukoencephalopathy, Other)

Obstetric and Gynecological History

- History of previous pregnancies (Yes/No)
- Number of previous pregnancies (1, 2, 3, 4, >4)
- Previous pregnancy outcome (Full term live birth, preterm live birth, spontaneous abortion, still birth, therapeutic abortion, elective abortion, ectopic pregnancy, unknown)

- Gestational Age (Weeks) as continuous and categorical (<23, 23-27, 28-32, 33-36, ≥37)
- History of adverse pregnancy outcomes (Yes/No)
- History of obstetrical complications during previous pregnancies (Yes/No)
- Type of obstetrical complication during previous pregnancies
- Reason for termination (if terminated)

Medical History

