Medical history of the women will be summarized in SAFW by System Organ Class (SOC) and Preferred Term (PT). For each previous and concurrent medical history recorded medical history (MH), the term entered by the investigator describing the event (the "reported term") will be assigned a standardized term (the "Preferred Term" [PT]) and assigned to a superclass term (the "System Organ Class" [SOC]) on the basis of the Medical Dictionary for Regulatory Activities (MedDRA) World Health Organization (WHO) dictionary of terms.

Previous and concurrent medical history will be also listed.

Vaccination History

Severe acute respiratory syndrome coronavirus 2 (SARS-CoV-2) vaccination history will be summarized in the SAFW overall and split by the period prior to infant's birth and before/after LMP and after infant's birth. Non-SARS-CoV-2 vaccination history will be summarized by pathogen (Appendix 5) in SAFW overall and split by the period prior to infant's birth and before/after LMP and after infant's birth. Where time period can't be determined due to completely or partially missing date, it will be imputed to before infant's birth.

SARS-CoV-2 vaccination history will also be listed in the SAFW, including the following:

- Manufacturer name (first, second and, if applicable, third dose and any booster dose[s]) (Pfizer/Biontech coronavirus disease of 2019 [COVID -19] vaccine, Moderna COVID -19 vaccine, Astra Zeneca COVID -19 vaccine, Johnson and Johnson Covid-19 vaccine, Other)
 - Type of vaccine for each dose (mRNA vaccine, Viral Vector Vaccine, Inactivated Vaccine, Other)
 - Timepoint of last COVID-19 vaccination prior to LMP (>6months before LMP, 3-6 months before LMP, <3 months before LMP, 1st trimester, 2nd trimester, 3rd trimester, ≤6 months postpartum, >6 months postpartum).

Other Vaccinations history (vaccines other than SARS-CoV-2) will also be listed in the SAFW.

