4.8.1 Exposure of Study Medication

Ocrelizumab will not be administered post-baseline until the infant's birth. Treatment with commercial ocrelizumab may be resumed at any time after birth for women who decide not to breastfeed. Some women may decide to resume treatment with ocrelizumab whilst breastfeeding. For those women, treatment with ocrelizumab should be restarted after collection of the infant blood sample at Week 6 of life (±7 days) if possible, but the decision is left to the discretion of the woman and the investigator.

Definitions

Dose: Ocrelizumab dose is given as one infusion or two infusions administered 2 weeks apart. Women will be considered to have received a dose of treatment if at least part of one infusion of that Dose (either Day 1 or Day 15 for dual infusions) was given.

Treatment duration (in weeks) for woman received OCR will be calculated as follows: [(Date of last contact* - Date of first postpartum dose) + 1] / 7

*Earliest 1) date of last OCR dose plus risk window of 6 months (182 days)2) date of death3) Clinical Cut-off Date

Exposure Analysis

The following measures of exposure of ocrelizumab will be summarized in the SAFW using descriptive statistics:

- Number of patients completing each dose type (Dose 1, full dose; Dose 1 split dose #1; Dose 1, split dose #2, Dose 2, full dose; Dose 3, full dose)
- Treatment duration (weeks)
- Number of doses received (Day 1 and Day 15 infusions are considered as one dose)

• Total cumulative dose (mg)

A corresponding listing will be produced.

MS treatment postpartum

- Type of DMT including ocrelizumab use postpartum
- Time (months) between delivery and first postpartum ocrelizumab as continuous and categorical (0-3 months, >3 and ≤6 months, >6 months)
- Number of women who received ocrelizumab dose postpartum
- Number of ocrelizumab doses postpartum
- Time (months) between first and second postpartum ocrelizumab dose

4.8.2 Adverse Events

All summaries of AEs will be presented separately for women and infants based on the respective Safety population. Adverse events will be presented overall and by timepoint (defined below). AEs will also be presented for subgroups based on OCR exposure prior to the study as list below, for infants and women separately:

- In 3-month interval of before/during pregnancy (3-6 months before LMP, 0-3 months before to LMP, during the 1st trimester)
- ≥3 months before to LMP vs <3 months prior to LMP and/or during pregnancy

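### SAP 4.8.7 tabulates concomitant medication only during pregnancy and during breastfeeding, so drugs given to never-breastfed or weaned infants fall in no planned summary.

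*SAP*

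**What the plan says.** SAP 4.8.7 begins: "Concomitant medications (defined as treatment started after baseline visit) will be summarized, for women and infants separately". It then says that this will be done "by frequency tables according to the ATC classification system using the WHO Drug dictionary during pregnancy and during breastfeeding separately". It names no overall table, no period for postpartum time without breastfeeding, and no listing. It does not say when breastfeeding begins or ends for this purpose.

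Protocol 6.5 is unrestricted: "Concomitant medications recorded during the study will be summarized using frequency tables". The opening of SAP section 4 gives the SAP's analyses precedence over the protocol's, so the narrower rule governs.

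Three other SAP provisions bear on women only:
- SAP 4.3.1, under Prior Medications, also provides that "concurrent medications (defined as treatment started on or after the LMP) will be summarized, by frequency tables". Section 4.3.1 applies to the women's full analysis set: "baseline disease characteristics of women will be summarized and listed for the FASW, unless otherwise stated".
- SAP 4.8.1 lists among the postpartum MS treatment summaries "Type of DMT including ocrelizumab use postpartum".
- SAP 4.3.1 summarizes maternal vaccinations "overall and split by the period prior to infant's birth and before/after LMP and after infant's birth".

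No section of the SAP other than 4.8.7 summarizes medications given to infants.

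**The concern.** SAP 4.8 names concomitant medication as one of its safety outcome measures, and the infants are the subjects whom the study exists to observe. The two periods in 4.8.7 make sense for a mother. Applied to an infant, one is empty and the other depends on how the child is fed.

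The result does not fit the rest of the infant safety plan. SAP 4.8.2 reports infant adverse events over all of follow-up, split at 28 days of age, and counts infections and serious infections without regard to feeding. Infections would therefore be shown for all infants at all ages, but the drugs used to treat them only while the infant was breastfed. In never-breastfed and weaned infants a reader could not set treatment beside infection counts.

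**Working it through.** No sample size, rate or confidence interval enters this point, and the plan gives no figure to reproduce. The check is to take each group and period and find which SAP summary covers it.

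**Are the drugs recorded, and do such infants exist?** Protocol 4.5.3.1 has infant medication changes recorded throughout the study, at Week 6, at Months 2 to 12 and at the final visit. The same section expects infants fed only formula and infants who are fully weaned. SAP 4.5.3 and 4.6.1 place formula-fed infants in a planned subgroup. The data and the infants are both expected.

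**Does the definition of concomitant exclude infant drugs?** No. The baseline visit is the mother's, at gestational Weeks 24 to 30, so every infant drug starts after it. Only the choice of periods limits the infant table.

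**Coverage on a literal reading:**

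| Subject and period | SAP 4.8.7 | Other SAP summary |
|---|---|---|
| Infant, while breastfed | yes | none |
| Infant, never breastfed | no | none |
| Infant, after weaning | no | none |
| Mother, pregnancy after baseline | yes | 4.3.1 |
| Mother, breastfeeding | yes | 4.3.1; 4.8.1 for DMTs |
| Mother, postpartum and not breastfeeding | no | 4.3.1 as worded; 4.8.1 for DMTs; 4.3.1 for vaccinations |

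Only the second and third rows have no summary at all. The last row is covered if the 4.3.1 table is read as written, since it sets a start (the LMP) but no end and no feeding condition.

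**Illustration of size for one infant.** Protocol 3.1.4 runs follow-up to about 13 months of age. The documents give no weaning ages, so those below are assumptions. Share covered = months breastfed / 13.
- Never breastfed: 0/13 = 0%
- Weaned at 3 months: 3/13 = 23%
- Weaned at 6 months: 6/13 = 46%
- Breastfed throughout: 13/13 = 100%

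These are shares of follow-up time for one infant. They do not estimate how many of the approximately 30 evaluable infants, or how many drug records, would be left out; the documents give no feeding frequencies from which to work that out.

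**The case against.** The strongest reply is that little is lost. Infant adverse events, including infections, are summarized over full follow-up in SAP 4.8.2 by age period and by maternal exposure, and serious events are listed. Medication tables are supporting context. The data are collected in any case, so a table can be added. All of this stands, and it is why the point is minor. It does not remove the gap: the SAP states a rule, and that rule omits part of a safety summary that the protocol describes without limit.

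It can also be said that the two periods were written with mothers in mind and that an overall infant table is intended. That may be so, but the sentence applies the periods to women and infants alike and offers no overall table.

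Two stronger readings are tempting. The first is that non-breastfeeding mothers also appear in no summary. The documents do not support this. As worded, the 4.3.1 table takes in their postpartum drugs, and their DMTs and vaccinations are summarized after birth whatever the feeding. Some doubt remains because the 4.3.1 text sits under a heading about prior medications within the baseline section. If its authors meant it to stop at enrollment, these mothers would lack a table for drugs other than DMTs and vaccines.

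The second is that the omitted families are mainly those with early postpartum ocrelizumab, so that the omission is selective. Protocol 3.1.3 does say "Treatment with commercial ocrelizumab may be resumed at any time after birth for women who decide not to breastfeed", and asks breastfeeding women to wait for the Week 6 sample. But that request applies only where possible and is left to the woman and investigator. Neither document gives restart or feeding frequencies. Nor do the documents show how a mother's restart would reach an infant whom she does not breastfeed. This remains an inference.

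**Conclusion.** The concern holds for infants. On the text of SAP 4.8.7, medications given to never-breastfed infants, and to any infant after weaning, fall in no planned summary. For mothers there is no gap if 4.3.1 means what it says, and a partial one if it is meant to end at enrollment; the SAP should say which applies.

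The finding rests on a literal reading of 4.8.7 and on the SAP's precedence over Protocol 6.5. The coverage percentages also depend on the assumed weaning ages. Severity is minor: a descriptive safety table is incomplete, and no endpoint, estimand or interval changes.

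**What to change.** In SAP 4.8.7:
- Infants: add an overall table from birth to end of study in the infants' safety set, and keep time while breastfed as a sub-table.
- Women: add an overall post-baseline table, divided into baseline to delivery and delivery to end of study, with breastfeeding as a split inside the second period.
- Define when breastfeeding begins and ends for these tables, how mixed feeding counts, and where a drug that spans weaning is placed.

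In SAP 4.3.1, state whether the table of drugs started on or after the LMP ends at enrollment or runs through the study.

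The cost is a few sentences of SAP text and a small number of added tables. No new data are needed, because infant medication and feeding status are already collected.

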4.9 MISSING DATA

All methods for handling missing data and associated sensitivity analyses are described above, section by section, for each endpoint. If not otherwise specified, missing values are not imputed.

Appendix 1 Protocol Synopsis

TITLE: A PHASE IV, MULTICENTER, OPEN-LABEL STUDY EVALUATING B-CELL LEVELS IN INFANTS POTENTIALLY EXPOSED TO OCRELIZUMAB DURING PREGNANCY – THE MINORE STUDY

PROTOCOL NUMBER:	MN42988
VERSION NUMBER:	3
EUDRACT NUMBER:	2021-000062-14
IND NUMBER:	100593
NCT NUMBER:	NCT04998812
TEST PRODUCT:	Ocrelizumab (RO4964913)
PHASE:	Phase IV
INDICATION:	Multiple Sclerosis
SPONSOR:	F. Hoffmann-La Roche Ltd

Background

The most recent report combining clinical trial and post-marketing experience suggests no increased risk of adverse pregnancy/fetal outcomes with ocrelizumab use, including in those pregnancies considered to have fetal ocrelizumab exposure (hypothetically, an embryo/fetus is considered exposed *in utero* if the last infusion of ocrelizumab was within 3 months of conception, during pregnancy, or if the date was unknown). However, very limited systematic data are available to date on laboratory outcomes (particularly B-cell levels) and infections in infants potentially exposed to ocrelizumab during pregnancy, and no information on their ability to mount immune responses.

Objectives and Endpoints

This study will evaluate the potential placental transfer of ocrelizumab in women with clinically isolated syndrome (CIS) or multiple sclerosis (MS) [in line with the locally approved indications] whose last dose of ocrelizumab was administered any time from 6 months before the last menstrual period (LMP) through to the first trimester (up to gestational Week 13) of pregnancy, and the corresponding pharmacodynamic effects (B-cell levels) in the infant. Specific objectives and corresponding endpoints for the study are outlined below.

Objectives	Corresponding Endpoints
Primary Outcome Measure	
• To evaluate whether infants potentially exposed to ocrelizumab during pregnancy present with postpartum B-cell depletion	 Proportion of infants with B-cell levels (CD19 + cells, absolute counts) below the LLN, measured at Week 6 of life
Secondary Outcome Measures	
• To evaluate B-cell levels in infants potentially exposed to ocrelizumab during pregnancy	 B-cell levels (CD19+ cells, absolute counts and percentage of lymphocytes) measured at Week 6 of life

Objectives	Corresponding Endpoints	
Secondary Outcome Measure (cont.)		
 To evaluate whether there is placental transfer of ocrelizumab from the mother to the infant 	 Serum concentration of ocrelizumab in the umbilical cord blood at birth (target time frame of blood sampling: within 1 hour after delivery) Serum concentration of ocrelizumab in the infant at Week 6 of life 	
• To evaluate whether infants potentially exposed to ocrelizumab during pregnancy are able to mount humoral immune responses to clinically relevant vaccines	 Mean titers of antibody immune response(s) to common childhood vaccinations with full or partial doses given prior to 1 year, which include responses to diphtheria, tetanus, pertussis, Hib, PCV-13, MMR, and HBV Proportion of infants with positive humoral response (seroprotective titers; as defined for the individual vaccine) to vaccines 	
 To evaluate the levels of ocrelizumab in the mother during pregnancy 	 Serum concentration of ocrelizumab in the mother during pregnancy (time frame of blood sampling: Week 24–30, Week 35) and at delivery (time frame of blood sampling: within 24 hours after delivery) 	
Safety Objectives		
 To evaluate the safety of ocrelizumab in the mother, and the safety of infants potentially exposed to ocrelizumab 	 Rate and nature of adverse events in the mother throughout the study, including changes in clinical and laboratory results Rate and nature of adverse events in the infant throughout the study, including infections and hospitalizations 	
 To evaluate pregnancy and neonatal outcomes 	 Proportion of pregnancies resulting in live births (term and preterm, with and without congenital anomalies), therapeutic abortions, or stillbirths Infant characteristics at birth, including but not limited to body weight, head circumference and length 	
Exploratory Objectives		
• To evaluate the infant's growth velocity and developmental milestones in the first year of life	 Assessment of growth velocity based on age-adjusted body length, weight and head circumference, using growth charts according to the WHO Child Growth Standards, as well as absolute values, at Months 2, 4, 6, 9, and 12 Assessment of child developmental milestones in the domains of communication, gross motor, fine motor, problem solving, and personal-social at Months 2, 4, 6, 9, and 12, using the ASQ-3 	
• To evaluate humoral immunity to clinically relevant pathogens in mothers during pregnancy	 Mean titers of antibody immune response(s) to vaccinations, measured in the third trimester (time frame of blood sampling: Week 35) Percentage of women with positive humoral response (seroprotective titers; as defined for the individual vaccine) to vaccines (time frame of blood sampling: Week 35) 	

Objectives	Corresponding Endpoints	
Exploratory Objectives (cont.)		
	• Note: Immune responses to the following may be included: measles, mumps, rubella, tetanus , diphtheria, pertussis, varicella zoster, Streptococcus pneumoniae , HBV, and SARS-CoV-2; along with nucleocapsid and spike protein titers; only for those mothers who have received the vaccine, as per local clinical practice)	
 To measure disease activity in mothers during pregnancy and postpartum 	 Number of MS relapses during pregnancy and postpartum (clinical relapses) Mean change from baseling in the EDSS seere over the 	
	 Mean change from baseline in the EDSS score over the course of the study 	
 To detect presence of neuroaxonal damage in the mother during pregnancy and postpartum 	 sNfL levels during pregnancy (second trimester [time frame of blood sampling: Week 24–30], third trimester [time frame of blood sampling: Week 35] and at delivery [time frame of blood sampling: within 24 hours after delivery]) and postpartum (in line with ocrelizumab administration timepoints) 	
 To evaluate the evolution of B-cell levels between birth and the first year of life 	• Trajectory (absolute and percentage changes) of B-cell (CD19 + cell) levels in the infant from Week 6 of life to 1 month after the first or second dose of MMR vaccine or Month 13 of age in case MMR vaccine is not planned to be administered	
ASQ-3=Ages and Stages Questi HBV=hepatitis B virus: Hib=Hen	onnaire, version 3; EDSS=Expanded Disability Status Scale; nophilus influenzae type b: LLN=lower limit of normal:	

HBV = hepatitis B virus; Hib = Hemophilus influenzae type b; LLN = lower limit of normal; MMR = measles, mumps, and rubella; MS = multiple sclerosis; PCV-13 = 13-pneumococcal conjugate vaccine; SARS-CoV-2 = severe acute respiratory syndrome coronavirus 2; sNfL = serum neurofilament light chain; WHO = World Health Organization.

STUDY DESIGN

DESCRIPTION OF STUDY

This is a prospective, multicenter, open-label study in women with CIS or MS (in line with the locally approved indications) receiving commercial ocrelizumab up to 6 months before the LMP or during the first trimester (up to gestational Week 13), due to accidental exposure, or in whom a decision to treat with ocrelizumab was taken as part of routine clinical practice.

Note on referral to sites: Pregnant and lactating women with MS are often treated in a decentralized way between specialized and non-specialized centers. It is difficult to predict at which clinical sites eligible women will be identified; and activation of new sites that identify potential women is not viable since it could take several months, and would not be achieved in time to screen the women while they still meet the protocol inclusion criteria. By using established networks and pregnancy registries for referral, the study could be completed in a timely manner. For these reasons, women may be referred to study sites; and study visits may be home-based (conducted by a mobile nurse, and by the investigator using telemedicine [i.e., remotely]). Implementation of these elements will depend on local requirements as well as agreement by the investigator, and capacity to use telemedicine. The investigators will be informed about the approach that may be used in their country.

The study will consist of the following periods.

- Screening/baseline period (between gestational Week 24 and 30): After providing written informed consent, women will enter a screening period between gestational Weeks 24 and 30, after the morphological scan (usually done at gestational Week 18–20). Women fulfilling the inclusion/exclusion criteria with accidental ocrelizumab exposure, or in whom a decision to treat with ocrelizumab was taken as part of routine clinical practice, will be enrolled; *some* of these women should have potential fetal exposure (i.e., have received their last dose of ocrelizumab <3 months before the LMP or during the first trimester [up to gestational Week 13]). Exposure to ocrelizumab includes administration of an initial split dose of two 300 mg infusions (in 250 mL 0.9% sodium chloride) separated by 14 days for women initiating treatment with ocrelizumab, or a single 600 mg infusion (in 500 mL 0.9% sodium chloride) for women already on treatment with ocrelizumab. The baseline visit will be combined with the screening visit. To reduce the burden of visits on the mothers, results from physical and obstetric examinations, as well as neurological examinations, done as part of routine care may be used. The scheduled obstetric blood glucose test should preferably be conducted at the screening/baseline visit rather than at a separate visit.
- Pregnancy and early postpartum period (up to Week 6 of life): Laboratory and clinical assessments during the third trimester (gestational Week 35 [±14 days]), will be performed in accordance with planned prenatal care visits, whenever possible. To reduce the burden of visits on the mothers, results from physical and obstetric examinations, as well as neurological examinations, done as part of routine care may be used. All visit samples may be collected by home nurse visit. At birth, a blood sample will be collected from the umbilical cord (only for live births; no collection should occur in the event of a pregnancy interruption [i.e., therapeutic abortion or stillbirth]). The target time frame for collection will be within 1 hour after delivery; the actual time of collection after delivery will be recorded. At week 6 (\pm 7 days) of the infant's life (or equivalent age for preterm births, i.e., gestational week at birth <37 weeks). At Week 6 (\pm 7 days) of the infant's life, a blood sample will be collected from the infant (at an on-site visit, or by a home nurse visit) for measurement of B-cell levels (the primary endpoint). Ocrelizumab must not be administered after the woman is enrolled in the study and until the infant's birth. Treatment with commercial ocrelizumab may be resumed at any time after birth for women who decide not to breastfeed. Some women may decide to resume treatment with ocrelizumab whilst breastfeeding. For those women, treatment with ocrelizumab should be restarted after collection of the infant blood sample at Week 6 of life $(\pm 7 \text{ days})$ if possible, but the decision is left to the discretion of the woman and the investigator.

If the woman switches to another DMT postpartum, the infant blood sample at Week 6 of life (\pm 7 days) will only be collected if the woman is not breastfeeding.

Vaccination period (after Week 6 of life and up to 1 month [+30 days] after the first or second dose of MMR vaccine, or at Month 13 of age [+30 days] if the MMR vaccine is not planned to be administered): Both mother and the infant will enter an extension phase, which will continue approximately until the infant reaches 13 months of age. This is designed to evaluate whether infants potentially exposed to ocrelizumab during pregnancy are able to mount humoral immune responses to clinically relevant vaccines. Infant laboratory assessments will be performed 1 month (+ 30 days) after the first dose of MMR vaccine (if first dose is administered at 11 months of age or later), 1 month (+30 days) after the second dose of MMR vaccine (if first dose is administered before 11 months of age), or at Month 13 of chronological age (+ 30 days) if MMR vaccine is not planned to be administered (as per local clinical practice, vaccinations may include *diphtheria*, tetanus, pertussis, Hib, PCV-13, HBV, and MMR). Additionally, infants will continue to be followed up for growth (age-adjusted body length, weight and head circumference) and developmental milestones up to 12 months of age. Growth charts following the WHO Child Growth Standards, absolute values and the ASQ-3 questionnaires will be used; other standard measurements recorded by e.g., the pediatrician as part of routine post-natal care may also be used. Post-natal timings of ocrelizumab infusions every 6 months and laboratory/clinical assessments in the mother may occur at different time points than infant assessments.

In case the mother decides to switch to another DMT or to stop DMT after birth, no laboratory/clinical assessments will be performed for the mother. However, the infant blood sample 1 month (+30 days) after the first or second dose of MMR vaccine (or at Month 13 of age [+30 days]) will still be collected.

- A structured telephone interview will be conducted by site personnel every 3 months
 postpartum (in-between ocrelizumab infusions) for a general review, and to identify and
 collect information on any changes in the woman's or infant's health status (including the
 occurrence of MS relapses in the woman and use of new concomitant medications) and
 possible adverse events in both the woman and the infant (particularly infections); women
 will also be asked if the ASQ-3 form is being filled out. No telephone contact is needed in
 weeks where the woman is performing on-site visits.
